1.0 Objectives / Specific Aims

The purpose of this project is to determine the efficacy of POWER training for treating post-stroke depressive symptoms. We will also determine if depression limits response to rehabilitation and the extent to which changes in depression are associated with improvements in functional performance post-stroke. The PI and Co-I's have experience performing all of the proposed methodologies. Specifically, we have extensive experience implementing exercise programs in persons post-stroke;^{13,31,32,36} performing assessments of post-stroke walking;^{13,36} and diagnosing and treating depression.^{37,38,39,40}

Aim 1: Determine the efficacy of POWER training for treating PSD

We hypothesize significant reductions in HRSD scores in both groups, with improvements following POWER greater than control. We also expect greater response and remission rates in the POWER group.

Aim 2: Determine the influence of PSD on the rate and extent of response to POWER training

We posit that POWER training-induced improvements will be attenuated, though still significant, in depressed subjects. In addition, we hypothesize that improvements in walking speed and lower extremity muscle power generation will be contingent upon improvements in HRSD and that a critical threshold will determine the point at which depression is reduced thereby facilitating functional improvements.

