3.0 Intervention to be studied

Emerging evidence suggests that resistance training is effective at reducing depressive symptoms.^{11,12,27} We developed an innovative rehabilitation approach, Post-stroke Optimization of Walking using Explosive Resistance (POWER) training; a high-velocity, high-intensity lower extremity resistance training intervention that improves post-stroke muscular and locomotor function (RR&D RX000844).¹³ Preliminary findings from this study suggest POWER training reduces symptoms in those with mild to moderate depression (Figure 1). We seek to build upon these findings to determine its efficacy (vs. control) in treating PSD.

Chronic stroke survivors with mild to moderate depression (n=32) will be randomly assigned to the intervention (POWER) or attention control (stretching) group. POWER training will take place over a 12-week period (3 sessions/week) with exercises including leg press, calf raises, and jump training, all performed at high concentric velocity, as well as trials of fast walking. We will perform bi-weekly measurements of depressive severity using the Hamilton Rating Scale for Depression (HRSD).

Chronic stroke survivors with mild to moderate depression (n=16) as well as age (± 5 yrs), gender and severity-matched (determined by walking speed) non-depressed stroke subjects (n=16) will complete 12 weeks of POWER training. We will perform bi-weekly HRSD measurements as well as comprehensive dynamometric assessments of paretic and non-paretic knee extensor muscle power generation and self-selected walking speed at these same time points. Secondary assessments of locomotor function will be the six-minute walk test (6MWT) and the amount of community walking measured via step activity monitors (SAM).

Stretching is being used as an attention control condition for POWER training. Control subjects will participate in a stretching protocol for the same duration (i.e. 60 minutes per session) and frequency (3 days per week) for 12 weeks to ensure that they have equal interaction with the study staff and controlling for the effects of repeated social interaction on depressive symptoms.

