12.0 Data Management

Data Analysis Plan: We will compare the effects of POWER training (vs. control) on HRSD scores. We will also determine response ($\geq 50\%$ reduction in symptoms) and remission ($\text{HRSD} < 10$) rates following training and at a six-month follow-up. We will utilize repeated measures mixed effects models to assess significant changes in outcomes between groups. Time and group will serve as dependent variables, as well as their interactions. A random intercept term will be included in the model to account for clustering within subjects. Various error structures associated with the repeated measures will be considered (e.g. compound symmetry vs. auto-regressive).

We will determine if PSD limits response to treatment by making between group comparisons of change (post-pre) in outcomes in depressed vs. non-depressed subjects utilizing repeated measures mixed models. Time (seven occasions), group (depressed vs. non-depressed) and their interaction will serve as dependent variables. Three primary dependent variables of interest here are, self-selected walking speed (SSWS) and paretic leg power generation. A random intercept term will be included in the model to account for clustering within subjects. Various error structures associated with the repeated measures over time will be considered (e.g. compound symmetry vs. auto-regressive). Analyses incorporating differences in outcomes as dependent variables will examine whether changes over time are more pronounced in depressed versus non-depressed subjects as well as whether changes are more pronounced in depressed subjects with the greatest improvement in HRSD. These models will also incorporate random subject effects to account for within-subject dependence. To determine associations between changes in outcomes, we will look at the relationships between outcomes using Pearson or Spearman correlations, depending on the distribution of the data. Further, we will use segmented (joint-point) regression to estimate if specific thresholds exist that mark in individual subjects where HRSD starts improving (decreases) and other outcomes start to improve (increase) to help us understand

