if there is a critical point of change in HRSD that is important for facilitating functional improvements. The purpose of using the segmented regression is to see if HRSD scores either plateau or change direction at a given point. The segmented regression model will essentially fit two linear models that have different slopes and intercepts but meet at a point of time. This will be achieved through inclusion of a dummy variable and its interaction with time in the model. The dummy variable will take the value 0 for time points below the threshold and 1 above. The threshold, namely the time, at which the model changes direction will be assumed unknown. Therefore, this model will be a non-linear regression model. We have written a macro in SAS to fit such models. This macro also allows for higher-order polynomials. Our intention is to fit random effects models, calling PROC NLMIXED in our macro. Other covariates can also be included in this approach. The purpose of the segmented regression model is to identify the earliest time at which there is maximum effect.

All efforts will be taken to minimize dropouts. If dropouts occur, we will attempt to determine the reason for dropout. If the dropouts occur at random, the mixed effects model can account for the missing data. However, if the dropouts are found to be treatment related, they will be treated as non-ignorable missing data and appropriate missing data methods will be applied and multiple imputations considered.

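### The segmented HRSD model locates a bend in scores, not a bend in the POWER-minus-stretching difference, so its knot should not be reported as the time of maximum effect

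*Combined protocol and SAP*

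**What the plan says.** The segmented regression is described in section 12.0 (Data Management, Data Analysis Plan). It follows directly on the depressed versus non-depressed comparison, whose factors are given as: "Time (seven occasions), group (depressed vs. non-depressed) and their interaction will serve as dependent variables". Under section 3.0 both groups in that comparison are trained with POWER. The depressed group is 16 subjects, and the matched "non-depressed stroke subjects (n=16) will complete 12 weeks of POWER training".

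The model has a join at an unknown time: "This will be achieved through inclusion of a dummy variable and its interaction with time in the model". Random effects are to be fitted. The only opening for further terms is optional: "Other covariates can also be included in this approach".

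The plan gives the model three purposes:
- to find a critical change in HRSD that precedes functional gains;
- a description of the score course: "The purpose of using the segmented regression is to see if HRSD scores either plateau or change direction at a given point";
- a timing claim: "The purpose of the segmented regression model is to identify the earliest time at which there is maximum effect".

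On the control arm, section 1.0 states: "We hypothesize significant reductions in HRSD scores in both groups, with improvements following POWER greater than control". Section 3.0 gives stretching the role of controlling for repeated contact with study staff, and schedules HRSD every two weeks in the randomised comparison. POWER is compared with stretching over time only in the separate Aim 1 mixed model (time, group, interaction), which is not linked to the knot.

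**The concern.** A bend in the HRSD scores of treated subjects and a maximum in the treatment effect are different quantities. The effect of POWER at a given week is the difference from stretching at that week. If scores in both arms fall early for a reason they share and then level off, scores under POWER will bend at that point even though the difference between arms is still growing, or is absent.

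The plan itself makes a shared fall plausible: it predicts improvement under stretching and includes that arm to absorb the effect of contact. The pilot cannot settle the matter because it had no comparison group.

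At stake is a secondary conclusion, the week by which POWER is said to have done its work. It could be reported too early, or reported for a component of response that is not due to POWER.

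**Working it through.** **Inputs from the plan.** Pilot HRSD means were 15.1 at baseline, 10.8 at week 6 and 8.5 at week 12 (section 2.0), a total fall of 6.6, of which 4.3 (65%) came by week 6. Section 12.0 gives a detectable difference of 2.94, SD 5.3, 13 completers per arm, AR(1) correlation 0.5 and 10 measurements. Seven occasions correspond to weeks 0, 2, …, 12.

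**The plan's own figure first.** The plan gives no figure for the knot. Its Aim 1 power reproduces approximately:
- The mean of 10 AR(1) measurements with correlation 0.5 has variance factor 0.26, so the SD is 5.3 × √0.26 = 2.70.
- The standard error of the difference is 2.70 × √(2/13) = 1.06.
- Power is Φ(2.94/1.06 − 1.96) = 79.2%, against the stated 80% (two-sided 5% assumed).

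So 2.94 is a minimum detectable difference, not a predicted benefit. It is used below only as a plausible size.

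**Illustration.** Assume a shared fall S complete by week 4, and a POWER-specific fall P complete by week w, with S + P = 6.6:
- stretching mean = 15.1 − S × min(t, 4)/4
- POWER mean = stretching mean − P × min(t, w)/w

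The main split takes P = 2.94, so S = 6.6 − 2.94 = 3.66. A joined two-line model was fitted to the seven noise-free POWER means, and separately to the differences, with AR(1) 0.5 weighting and knots on a 0.25-week grid.

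| Assumed course | POWER-only knot (weeks) | Difference peaks (weeks) | Difference at the POWER-only knot |
|---|---|---|---|
| S 3.66; P 2.94 complete at week 8 | 4.5 | 8 | 2.94 × 4.5/8 = 1.65 |
| S 3.66; P 2.94 complete at week 10 | 4.25 | 10 | 2.94 × 4.25/10 = 1.25 |
| S 3.66; P 2.94 linear to week 12 | 4.0 | 12, no knot | 2.94 × 4/12 = 0.98 |
| S 3.66; P 2.94 starting after week 4 | 4.0 | 12 | 0 |
| S 6.6; P 0 | 4.0 | no effect | 0 |
| S 1.5; P 5.1 complete at week 8 | 7.25 | 8 | 5.1 × 7.25/8 = 4.62 |
| S 0; P 6.6 complete at week 8 | 8.0 | 8 | 6.6 |

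Unweighted least squares on a finer grid moves the first two knots to 4.63 and 4.29, so the range for the main split is about 4 to 4.6.

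The third row can be checked by hand. The slope is −3.66/4 − 2.94/12 = −1.16 per week up to week 4 and −2.94/12 = −0.245 afterwards, so the bend is exactly at week 4.

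**With sampling noise** (13 per arm, SD 5.3, AR(1) 0.5, 1,000 runs). The POWER-only knot fell at or before week 5 in 56–59% of runs in the first three rows and in 81% when the whole fall was shared. It did so in 36% with the small shared fall and 29% with none, so part of the early placement is noise. With 1,000 per arm in the first row, the POWER-only knot stays at a median of 4.5 while the knot of the difference has median 8.0. The gap is therefore a matter of target, not sample size.

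**Precision of the corrected target.** With 13 per arm the knot of the difference has an interquartile range of about 3 to 9 weeks. Taking 5.3 as the SD at a single visit, the 95% half-width of one between-arm difference is 1.96 × 5.3 × √(2/13) = 4.1 points, which exceeds 2.94.

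**The case against.** The model's leading purpose is a within-person threshold linking HRSD change to functional gain. That question does not in itself need a control arm, and the criticism rests on one closing sentence. The Aim 1 time-by-group model already supplies a randomised time course. The illustration also returns what was put in: the shared fall ending at week 4, and its size of 3.66, are assumptions found nowhere in the documents. Most of the assumed courses fall faster than the pilot: the first three rows give week-6 means of 9.24, 9.68 and 9.97 against 10.8, and only the late-start row (10.70) is close. The fits use group means, whereas the plan intends a random-effects model.

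All of this stands as a limit on size and scope. It does not remove the mismatch between what the knot measures and what it is said to identify, because nothing in the plan ties the knot to the Aim 1 model.

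A reader might infer three stronger things that the documents do not support:
- **That stretching subjects are excluded from the segmented model.** This follows only from its placement and its listed terms. Pooling both arms without an arm term would still not time a POWER effect.
- **That the plan attributes control-arm improvement to the passage of time or regression to the mean.** It names only social interaction.
- **That the reported week will be wrong, or will set the length of a later programme.** Neither is stated or derivable.

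**Conclusion.** The point holds as a mismatch between the stated purpose and the quantity estimated. As written, the knot describes when HRSD scores bend in a group that, by the model's placement, all receive POWER. It can be read as the time of maximum effect only if there is no shared improvement, or if that improvement has little influence on the bend. The plan predicts improvement under stretching but gives no information on its size or timing.

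The displacement is therefore conditional. With the assumed 3.66-point shared fall by week 4 it is 3.5 weeks when the effect peaks at week 8 (8 − 4.5), 5.75 weeks at week 10 (10 − 4.25) and 8 weeks at week 12 (12 − 4). It falls to 0.75 week with a 1.5-point shared fall and to zero with none. The Aim 1 primary comparison is untouched, and so is the use of the model for the HRSD-function threshold. The fault is confined to the timing conclusion.

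**What to change.** In section 12.0:

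1. State which subjects and arms enter the segmented model. Describe a POWER-only knot as a within-group HRSD plateau, keep it for the HRSD-function threshold question, and delete the sentence that equates it with the time of maximum effect.
2. Base any statement on the timing of the treatment effect on the POWER-minus-stretching HRSD difference at each bi-weekly visit in the two randomised arms. Take it from the Aim 1 time-by-group model with visit-specific contrasts, or from a joint segmented fit with arm-specific slopes, and give an interval (for example by resampling subjects within arm).
3. Define the quantity in advance, including what will be reported if the fitted difference is still growing at week 12, when no earlier maximum exists.
4. Label the result exploratory.

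The cost is SAP wording and arm terms in the existing macro. The HRSD visits are already scheduled, so no new data are needed. The real price is precision: with about 13 completers per arm the timing may be nearly uninformative, and the report should say so. This applies to HRSD. Section 10.0 schedules dynamometry during POWER, so the same contrast may not be available for muscle power.

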extremity muscle strength and power were accompanied by improvements in self-selected as well as fastest comfortable walking speeds. Specifically, strength increased by 25.0 and 23.3 percent in the paretic and non-paretic plantar flexor (PF) muscle groups, respectively. Improvements in knee extensor (KE) strength were not as large, with gains of 14.8 percent in the paretic side and 16.0 percent in the non-paretic side. Gains in KE peak power of 28.6 and 30.7 percent in the paretic and non-paretic limbs, respectively, were also found post-training. Self-selected walking speed increased from 0.71 to 0.92 m/s, exceeding the clinically meaningful difference reported for participants post-stroke. Fastest comfortable walking speed increased from 1.10 to 1.51 m/s.

POWER training improves depressive severity:

We have enrolled and trained 10 subjects to date with mild to moderate PSD in POWER training. We measured depression severity (HRSD), at pre-, mid- and post-training time points over the 12 week training period. HRSD scores prior to training (15.1 ± 7.5) decreased after 6 weeks (10.8 ± 4.3) and 12 weeks (8.5 ± 3.3) of training. In addition, 7 subjects realized a $>50\%$ reduction in depression severity (i.e. response) and 8 were considered to have achieved remission (i.e. HRSD < 10). Although we did not have a comparison group with PSD in this pilot study, these data suggest the potential for POWER training to positively impact depression severity in individuals with PSD.

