Sample size determination and Statistical Approach: A total of 50 post-stroke subjects will be recruited. For Aim 1, 32 subjects with PSD will participate in either POWER training or control intervention (n=16 per group). These analyses will rely on longitudinal measures and we assume (based on experience with this intervention) that no more than 15% will fail to complete all assessments. This is an extremely conservative approach in that none of the subjects in our pilot trial withdrew from treatment. With 16 subjects enrolled per group and a 15% attrition rate over time (resulting in complete data on 13 subjects per group), we would have at least 80% power to detect a minimum difference in the change in HRSD from baseline to the end of the study of 2.94 (change in pilot data = 6.6) with a s.d. of 5.3 (at 5% significance level). Since this is a longitudinal study, we also incorporated an autocorrelation (AR(1)) of 0.5 for 10 measurements within individuals. The published studies report treatment effect sizes ranging from 0.6 to 0.9, which are more conservative. In our preliminary data, we observed an effect size of 1.19 (95% CI 0.98 to 1.36) for improvement in depression severity. To detect this effect we will have more than 90% power. For Aim 2, with baseline data from n=26 subjects, we will have 80% power to detect a minimum difference (pre-post) of 0.13 m/s for SSWS (s.d. = 0.2 m/s) and 17.88 ft/lb for muscle strength (s.d.=31.9 ft/lb) using a longitudinal approach with an autocorrelation (AR (1)) of 0.5 for 10 measurements within individuals. In the statistical analysis for both aims, we will summarize the longitudinal data using Spaghetti plots. If the spaghetti plots suggest linear or quadratic trend we will include these in the model along with appropriate interactions and random effects. We will perform appropriate model diagnostics and, if needed, consider transformations to achieve normality. To reduce potential heterogeneity in the data, secondary analysis will adjust for covariates such as depression level.

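### The pilot effect of 1.19 comes from 10 subjects with no control arm: its stated interval is about 3 to 5 times too narrow, and power to detect it is not power for a plausible POWER-versus-control difference

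*Combined protocol and SAP*

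**What the plan says.** Section 12.0 (sample size paragraph) makes two separate power statements for Aim 1.

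- **Main statement.** With 16 enrolled and 13 complete per group, the plan claims "at least 80% power to detect a minimum difference in the change in HRSD from baseline to the end of the study of 2.94", citing "change in pilot data = 6.6) with a s.d. of 5.3" at the 5% level. It assumes an AR(1) autocorrelation of 0.5 over 10 measurements.
- **Second statement.** After noting published treatment effects of 0.6 to 0.9, which it calls more conservative, the plan says "we observed an effect size of 1.19 (95% CI 0.98 to 1.36) for improvement in depression severity" and then "To detect this effect we will have more than 90% power".

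The source of the pilot effect is in section 2.0: "We have enrolled and trained 10 subjects to date with mild to moderate PSD in POWER training". The results were: "HRSD scores prior to training (15.1 ± 7.5) decreased after 6 weeks (10.8 ± 4.3) and 12 weeks (8.5 ± 3.3) of training". The fall of 15.1 − 8.5 = 6.6 is the pilot change quoted in section 12.0, so this is the same pilot. Section 2.0 also concedes that "we did not have a comparison group with PSD in this pilot study".

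Section 1.0 states the expectation for the trial itself: "We hypothesize significant reductions in HRSD scores in both groups", with a larger improvement after POWER.

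**The concern.** Two things look wrong.

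1. **Precision.** An interval of width 0.38 around a standardised effect is far tighter than 10 subjects can give. Its lower limit of 0.98 lies above the top of the published range (0.9), so the pilot appears to show clearly that this intervention does better than earlier studies.
2. **Kind of effect.** A change within one treated group includes regression to the mean, natural recovery and the effect of attention. Aim 1 compares POWER with an attention control designed to absorb some of that. If the control arm also improves, as the plan expects, the between-group effect is smaller than the pre-post effect by the amount of the control-arm change.

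A reader who takes the two sentences at face value would conclude that the trial is comfortably powered for an effect already measured with good precision. Neither part of that conclusion is supported.

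**Working it through.** **Inputs.** Pilot n = 10, HRSD 15.1 (SD 7.5) to 8.5 (SD 3.3) (section 2.0). Change 6.6, SD 5.3, effect 1.19 (0.98 to 1.36), 13 completers per group, AR(1) 0.5, 10 measurements, 5% level (section 12.0). Sidedness is not stated; two-sided is assumed.

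**1. Reproducing 1.19.** 6.6 / 5.3 = 1.245. The usual small-sample correction with 18 degrees of freedom is 1 − 3/(4 × 18 − 1) = 0.958, and 1.245 × 0.958 = 1.19. The point value can therefore be obtained from the plan's own figures, although the plan does not say that this was the method.

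**2. Reproducing the power figures.** The mean of 10 AR(1) measurements with correlation 0.5 has variance factor f = (1/10) × [3 − 0.4 × (1 − 0.5^10)] = 0.26. The standard error of a group difference, in SD units, is √(0.26 × 2/13) = 0.20.

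- Detectable difference at 80% power: (1.96 + 0.84) × 5.3 × 0.20 = 2.97, against 2.94 stated. Power at 2.94 is 79%.
- The same formula gives 17.88 for the Aim 2 strength figure (SD 31.9), as stated. It gives 0.11 m/s for walking speed, against 0.13 stated. It is very likely, but not certain, that this is the plan's method.
- At 1.19: 1.19/0.20 − 1.96 = 3.99, so power is over 99.9%. The claim of more than 90% is reproduced.

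**3. The interval.** The stated width is 1.36 − 0.98 = 0.38, which implies a standard error of 0.38/3.92 = 0.097. For a mean change in units of its own SD with n = 10:

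- Normal approximation: SE = √(1/10 + 1.19²/20) = 0.413. Interval 0.38 to 2.00, width 1.62, which is 4.3 times the stated width.
- Noncentral t: 0.35 to 1.99, width 1.65, 4.3 times. If 1.19 is a bias-corrected 1.245, the interval from 1.245 is 0.39 to 2.07.

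Other choices of standardiser and formula:

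| Approach, n = 10 | Width relative to 0.38 |
|---|---|
| Simplest correlation-scaled formula | 2.8 to 3.1 |
| Raw-score SD, equal variances | 3.4 to 3.6 |
| CI of mean change divided by SD | 3.8 |
| Raw-score SD, observed variances | 4.2 to 4.3 |
| Pre and post treated as independent groups | 5.0 |

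The rows that depend on correlation use 0.74 to 0.79. SDs of 7.5, 3.3 and 5.3 imply (56.25 + 10.89 − 28.09)/(2 × 7.5 × 3.3) = 0.79; the SD that 1.19 would imply without a correction, 6.6/1.19 = 5.55, implies 0.74. The most favourable formula reaches a width of 0.38 only at a correlation of about 0.97. By the normal approximation, a width of 0.38 needs about 182 subjects.

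**4. Power for a between-group effect.** 13 per arm, two-sided 5%. The second column is a two-sample t test on a single change score, taking the SD as that of the change. The third is the formula of step 2.

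| Effect (SD units) | Single baseline-to-week-12 change score | AR(1) mean of 10 |
|---|---|---|
| 0.55 (2.94/5.3) | 27% | 79% |
| 0.6 | 31% | 85% |
| 0.9 | 60% | 99% |
| 1.19 | 83% | over 99.9% |

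**The case against.** The strongest reply is that nothing important depends on these two sentences. The interval enters no calculation. The main Aim 1 statement uses 2.94 points (0.55 SD), less than half the pilot change and below the published 0.6 to 0.9. The paragraph does not explicitly use the interval to dismiss the published range. All of this stands, and it limits the reach of the point.

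Three stronger readings are tempting, and the documents do not support them.

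- **That 1.19 is inconsistent with 6.6 and 5.3.** The uncorrected ratio is 1.245, but a common small-sample correction gives 1.19. All that can be asked is that the derivation be named.
- **That the power claim is an arithmetic error and should read 83%.** Under the plan's AR(1) assumption the claim reproduces with room to spare. The 83% answers a different question, namely power for a single change score, which is how section 4.0 words the primary outcome (HRSD change from baseline to week 12). Section 12.0 plans a repeated-measures mixed model.
- **That 0.35 to 1.99 is the one correct interval.** The standardiser is undocumented, so the exact limits and the multiple vary.

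None of this rescues the stated interval, which no plausible formula gives for 10 subjects, or the use of a non-comparative effect in a two-arm power claim.

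**Conclusion.** The point holds in two parts. The interval of 0.98 to 1.36 is about 3 to 5 times too narrow for a pilot of 10. One computed for that size runs from roughly 0.35 to 2.0 and takes in the whole published range, so the pilot gives no ground for treating 0.6 to 0.9 as pessimistic. And 1.19 is a single-arm pre-post change, so the claimed power to detect it is not power for a plausible POWER-versus-control difference.

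The fault is in the input and its stated precision, not in the power arithmetic. The sample size is not shown to be wrong by this point, because the 80% statement does not use 1.19. What the paragraph does lack is a declared basis. The same effects give 31% to 60% or 85% to 99%, according to whether one change score or an average of 10 correlated measurements is analysed. These figures assume two-sided 5%, 13 completers per arm and, for the change score, an SD of change of 5.3.

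**What to change.** In section 12.0:

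1. Replace the interval with one computed for n = 10 (about 0.35 to 2.0), and name the formula behind it and behind 1.19.
2. Label 1.19 as a single-arm pre-post effect.
3. Delete the sentence claiming more than 90% power, or restate it for a between-group effect such as the published 0.6 to 0.9, naming the method.
4. Use one basis throughout the paragraph. If the change score is chosen, the statement at 2.94 must be restated too (about 27%). If the AR(1) average is kept, say so and say what contrast it estimates. Mixing the two would make the paragraph contradict itself.

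The cost is a few sentences and some less favourable figures. No patients, visits or data are added.

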Following RMT assessment, we will assess the participant's $\text{SI}_{1\text{mV}}$. The same 'hotspot' location and SA-PEST procedure will be used to determine the participant's $\text{SI}_{1\text{mV}}$, however the SA-PEST program will be set to search for MEP amplitudes of approximately 1-mV. Once established, the $\text{SI}_{1\text{mV}}$ will be used as a primary measure of corticospinal excitability. Using the %MSO of the $\text{SI}_{1\text{mV}}$ we will then collect 20 test MEP's at a rate of 0.25Hz. Once MEP's are collected, participants will be set-up for peripheral nerve stimulation. Stimulation of the median nerve of the non-dominant arm will be delivered via constant current stimulator (DS7A; Digitimer, Hertfordshire, UK). Bipolar electrodes will deliver a $200\mu\text{s}$ square wave pulse at an intensity equal to 300% sensory perceptual threshold. Perceptual threshold will be determined each session and will be defined before any stimulation protocols are commenced. Single pulse TMS will be applied to the APB muscle representation on the contralateral motor cortex 25ms (ISI25) after the delivery of median nerve stimulation. A train/delay generator (Digitimer, Hertfordshire, UK) will trigger paired peripheral nerve stimulation and brain stimulation. A total of 200 paired stimuli will be delivered at rate of 0.25 Hz, resulting in a total stimulation time of ~14 minutes. The 20 test MEP's will be reassessed immediately after PAS, and then every 15 minutes for one hour.

We will utilize the PAS measures at baseline, after 2,4,6,8,10 and 12 weeks of treatment (or control) as well as at the follow-up time point to assess whether the interventions change PAS measured neuroplastic potential. We will use PAS to assess cortical excitability ($\text{SI}_{1\text{mV}}$) as well as neuroplastic potential (represented by mean normalized post-stimulation MEP amplitude). We will compare PAS measures at baseline to after either POWER or control. We will also compare repeated PAS measures in patients with and without PSD (Aim 2) to determine whether PSD inhibits neuroplasticity, and if effective treatments reverse the impaired potential for plasticity.

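### Power for both aims assumes 10 measurements per subject, but the plan schedules 7 (8 with follow-up), so power at the stated HRSD and strength differences is about 67–72%, not 80%

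*Combined protocol and SAP*

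**What the plan says.** The sample size paragraph in section 12.0 (Data Management) covers both aims.

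- **Aim 1:** 16 are enrolled per group with 15% attrition, "resulting in complete data on 13 subjects per group". The claim is "at least 80% power to detect a minimum difference in the change in HRSD from baseline to the end of the study of 2.94", "with a s.d. of 5.3 (at 5% significance level".
- **Aim 2:** data from 26 subjects, with 80% power for "0.13 m/s for SSWS (s.d. = 0.2 m/s) and 17.88 ft/lb for muscle strength (s.d.=31.9 ft/lb".
- **Both aims:** an "autocorrelation (AR(1)) of 0.5 for 10 measurements within individuals".

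The number of measurements appears elsewhere as follows.

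- The analysis plan in section 12.0 gives the depressed versus non-depressed model as "Time (seven occasions").
- Section 3.0 sets bi-weekly HRSD over the 12-week programme, and measures knee extensor power and walking speed at the same visits.
- Section 10.0 lists the visits for the paired associative stimulation measures: baseline, then "after 2,4,6,8,10 and 12 weeks of treatment (or control) as well as at the follow-up time point".
- Section 12.0 also assesses HRSD response and remission at a six-month follow-up.

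Section 4.0 defines the primary outcome as the absolute change in HRSD from baseline to week 12.

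**The concern.** Averaging more correlated measurements per subject shrinks the standard error. A calculation that assumes more measurements than will be taken therefore overstates power. Baseline plus weeks 2, 4, 6, 8, 10 and 12 is 7 occasions, and the follow-up makes 8. The document describes no schedule of 10. HRSD is the primary outcome, so the trial's main power claim rests on visits that are not planned.

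The Aim 2 sentence also looks uneven. The same subjects, correlation, number of measurements and power should give the same standardised difference for both outcomes. The printed values give 0.13/0.2 = 0.65 for walking speed and 17.88/31.9 = 0.56 for strength.

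**Working it through.** **Inputs, all from section 12.0 unless marked.** SDs are 5.3 (HRSD), 31.9 ft/lb (strength) and 0.2 m/s (walking speed). AR(1) correlation is 0.5, alpha 5% and power 80%. There are 13 per group in Aim 1. Inferred: a two-sided test, 26 in Aim 2 meaning 13 per group, and a contrast of group means averaged over all occasions.

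**Formula.** For m equally spaced occasions, the variance of a subject's mean is SD² × f(m), where f(m) = [sum over i, j of 0.5^|i−j|] / m².

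- f(10) = 26.004/100 = 0.2600
- f(8) = 20.016/64 = 0.3127
- f(7) = 17.031/49 = 0.3476

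Detectable difference = (1.960 + 0.842) × SD × √(f(m) × 2/13) = 1.0989 × SD × √f(m).

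The multiplier of SD is 0.5604 at m = 10, 0.6145 at m = 8 and 0.6478 at m = 7.

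**Reproducing the plan's figures at m = 10.**

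- Strength: 0.5604 × 31.9 = 17.88 ft/lb, as stated.
- HRSD: 0.5604 × 5.3 = 2.97, against 2.94 stated (power at 2.94 is 79.2%).
- Walking speed: 0.5604 × 0.2 = 0.112 m/s, against 0.13 stated (power at 0.13 is 90.1%).

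The strength match indicates that 10 entered the calculation and is not merely a misprint.

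**The same formula at the scheduled number of occasions.** Power = Φ(difference / (SD × √(f(m) × 2/13)) − 1.960). For example, HRSD at m = 7 has standard error 5.3 × √(0.3476 × 2/13) = 1.226, so power = Φ(2.94/1.226 − 1.960) = Φ(0.439) = 67.0%.

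| Outcome (stated difference) | Power, m = 10 | m = 8 | m = 7 | Detectable at 80%, m = 10 | m = 8 | m = 7 |
|---|---|---|---|---|---|---|
| HRSD (2.94) | 79.2% | 71.5% | 67.0% | 2.97 | 3.26 | 3.43 |
| Strength (17.88 ft/lb) | 80.0% | 72.4% | 67.9% | 17.88 | 19.6 | 20.7 |
| Walking speed (0.13 m/s) | 90.1% | 84.2% | 80.3% | 0.112 | 0.123 | 0.130 |

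**Effect of rounded SDs.** The walking-speed SD is printed to one decimal, so it could lie between 0.15 and 0.25. At m = 10 that range gives 0.084 to 0.140 m/s, and any SD from 0.223 to 0.241 gives a value that rounds to 0.13. If the SD were 0.232, walking-speed power at m = 7 would also be about 68%. An HRSD SD of 5.25, which can print as 5.3, gives 0.5604 × 5.25 = 2.94.

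**Baseline-to-week-12 change.** A plain two-group comparison of this change does not gain from the visits in between. Assume, since the plan does not say so, that 5.3 is the SD of the change. With 13 per group:

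- Normal approximation: detectable difference 1.0989 × 5.3 = 5.82 points, and power at 2.94 is 29%.
- t test: detectable standardised difference 1.145, so 1.145 × 5.3 = 6.07 points, and power at 2.94 is 27%.

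**The case against.** Four points can be made in the plan's favour.

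1. **The formula is inferred.** The plan does not name a time-averaged contrast, a two-sided test or a 13/13 split for Aim 2. The HRSD match is approximate and not unique: 16 per group with 8 measurements gives 2.936. This stands as a limit on certainty about the exact percentages. It does not touch the mismatch between 10 and 7 or 8, which needs no formula.

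2. **Aim 1 may have 8 occasions.** The statement of seven occasions belongs to the Aim 2 model, and HRSD response is assessed at follow-up. This stands, so both cases are shown. Even at 8, HRSD and strength fall short of 80%.

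3. **The three figures may share one design.** A reader might infer from 0.65 versus 0.56 that the walking-speed figure was computed with 7 measurements and the others with 10. The documents do not establish that. With rounding of the SDs, a single 10-measurement calculation can give all three.

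4. **Not every outcome loses power.** A reader might also infer that none of the stated power is available. That is too broad. With its printed SD, 0.13 m/s has 80.3% power at 7 occasions and 84.2% at 8.

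The plan also cites a pilot HRSD change of 6.6, well above 3.43. That was a change within one group without a comparator, so it does not show the size of a between-group difference.

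**Conclusion.** The power statement for both aims uses a number of measurements that the plan does not schedule. On the formula that best reproduces its figures, power for 2.94 HRSD points and 17.88 ft/lb is about 67–68% with 7 occasions and about 72% with 8. Restoring 80% at those differences would take 18 completers per group with 7 occasions, or 16 with 8, against the 13 assumed. The mismatch in measurements is certain. The percentages rest on the time-averaged contrast, the two-sided test and 13 per group in each aim.

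For walking speed, the finding is only that the printed inputs do not give 0.13 m/s at 10 measurements and that its derivation should be shown.

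The time-averaged contrast is also not the quantity that section 4.0 names as primary. The 27–29% power for the change to week 12 is conditional on reading 5.3 as the SD of change, and should not be quoted without that condition.

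**What to change.** In the sample size paragraph of section 12.0:

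- Replace the 10 measurements by the scheduled number for each aim, and say whether the follow-up counts.
- Restate all three detectable differences from the same unrounded SDs. With the printed SDs they are 3.43 HRSD points, 20.7 ft/lb and 0.130 m/s for 7 occasions, or 3.26, 19.6 and 0.123 for 8.
- Show the derivation of the walking-speed figure, with its SD to enough decimals.
- State the formula, the sidedness of the test and the number per group in Aim 2, and say that these are time-averaged contrasts.
- Beside them, give the detectable difference for the baseline-to-week-12 change in HRSD, and state which SD it uses. If 5.3 is the SD of that change, the figure is about 5.8 to 6.1 points.

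The cost is a rewritten paragraph and less favourable stated figures. Enrolment and visits stay as they are.
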